# 1. Study Synopsis: HCL Randomized Controlled Trial

Full title	Outpatient use of hybrid closed loop insulin management for type							
GI 4417	1 diabetes, a multi-centre randomized controlled trial.  Hybrid Closed Loop (HCL)							
Short title	·							
Clinical Trial Phase	III NY/A							
IND Sponsor (If Applicable)	N/A							
Chief Investigators	[name] [name], Associate [name]							
Subject Number Summary of eligibility criteria	12-25  yrs.  n=160							
Summary of engionity Criteria	
 
Type 1 diabetes (diagnosis consistent with American Diabetes Association Classification of Diabetes Mellitus) diagnosed at least 1 year ago
 
Fasting C peptide <0.1nmol/L (in the absence of hypoglycaemia)
 
Insulin regimen either: Multiple daily injections (MDI) ≥4 injections per day (≥3 rapid-acting insulin and ≥1 long-acting insulin), or insulin pump therapy (CSII) established for >3months.
 
Aged 12-<25years
 
HbA1c ≤10.5%
 
Living in an area with internet and cellular phone coverage
 
English speaking
 
							
Summary of exclusion criteria	1. Chronic kidney disease (eGFR <45mL/min/1.73m  )							
	
 
Use of any non-insulin glucose-lowering agent within the past 3 months
 
Oral or injected steroid use within the past 3 months
 
Pregnancy, or planned pregnancy within study period
 
Uncontrolled coeliac disease (not following a gluten free diet), or other untreated malabsorption
 
Uncontrolled thyroid disease
 
Clinically-significant gastroparesis
 
Uncontrolled hypertension (DBP >100 mmHg and/or SBP >160 mmHg)
 
History of myocardial infarction, severe uncontrolled heart failure, unstable angina, transient ischaemic attack (TIA), stroke, or thromboembolic disease in the past 3 months.
 
Poor visual acuity precluding use of the investigational technology
 
Inability or unwillingness to meet protocol requirements (including carbohydrate-counting, CGM use as per allocated study group only).
 
Severe or unstable medical or psychological condition which, in the opinion of the investigator, would compromise the ability to meet protocol requirements
 
							
Study Design	HCL vs. standard therapy (MDI and CSII), Australian multicentre parallel design study.  Participants will be randomized to use HCL or continue on standard therapy( MDI and CSII)  Minimisation randomisation will be employed, stratifying by time in target glucose range 3.9-10 mmol/L, age, diabetes duration, and centre site.							

	Duration of study – 7 months							
	Enrolment period – 12 months							
Investigational device	MiniMed™ 670G Insulin Pump Hybrid Closed Loop System.							
Hypothesis	1. HCL will increase time in sensor glucose target range (3.9 –							
	10mmol/L) compared to standard therapy.							
	2. HCL will reduce time spent in hypoglycaemic range							
	(<3.9mmol/L) compared to standard therapy.							
	3.HCL will improve glycaemic control as assessed by HbA1c.							
	4. HCL will have a positive impact on quality of life and fear of							
	hypoglycaemia as determined by participant/parent questionnaires							
	5. HCL will be a cost effective intervention for the management of							
Duimour abiactiva	type 1 diabetes compared to standard treatment.  1. The primary objective is to compare the proportion of time							
Primary objective	spent in target glycaemic range (sensor glucose level 3.9 - 10							
	mmol/l) while using HCL or using standard therapy (MDI and							
	mmol/l) while using HCL or using standard therapy (MDI and CSII).							
Secondary objectives	The secondary objectives are to compare the efficacy of the							
٠٠٠٠	MiniMed™ 670G Insulin Pump Hybrid Closed Loop System							
	versus standard therapy (MDI and CSII) by the measurement of							
	the following:							
	1.Glycaemic(24hr, day (0600 – 2400), night (0000 – 0600))							
	CGM data will be collected in three time blocks; baseline (3 weeks							
	CGM), 13 weeks (2 weeks CGM) and 26 weeks (3 weeks CGM)							
	post randomisation. A sub analysis of HCL vs. MDI and HCL vs.							
	CSII is planned.							
	i. CGM data:							
	a. % CGM Time <2.8 mmol/L							
	a. % CGM Time <2.8 mmol/L b. % CGM Time <3.3 mmol/L							
	c. % CGM Time <3.9 mmol/L							
	d. % CGM Time 3.9-7.8 mmol/L							
	e. % CGM Time >10.0 mmol/L							
	f. % CGM Time >13.9 mmol/L							
	g. % CGM Time >16.7 mmol/L							
	h. Standard Deviation and Coefficient of Variation							
	of CGM values							
	i. Mean CGM glucose							
	ii. Average Fasting blood glucose (mmol/L), as measured							
	during the three CGM time blocks at baseline, 13 weeks and 26 weeks. Defined as fasting capillary blood glucose							
	level on waking (between 5am and 9am), at least 6 hrs							
	after an insulin bolus for carbohydrate.							
	iii. Average Glycaemic control as measured by HbA1c							
	collected at baseline, 13 weeks and 26 weeks post							
	randomisation.							
	iv. Hospitalisations rate for diabetic ketoacidosis over the 7							
	month study period.							
	v. Episodes of severe hypoglycaemia over the 7 month study							
	period (defined having altered mental status and cannot							
	assist in their care, is semiconscious or unconscious, or in coma ± convulsions and may require parenteral therapy							
	* * * * * * * * * * * * * * * * * * * *							
	(glucagon or i.v.glucose).							

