## 1. Glycaemic(24hr, day (0600 – 2400), night (0000 – 0600))

CGM data will be collected in three time blocks; baseline (3 weeks CGM), 13 weeks (2 weeks CGM) and 26 weeks (3 weeks CGM) post randomisation. A sub analysis of HCL vs. MDI and HCL vs. CSII is planned.

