# 7 Design of the randomized controlled trial

# 7.1 Statement of design and randomisation

This is a prospective, randomized multi-centre study in adult and paediatric subjects from Australia, with type 1 diabetes mellitus aged 12 – 25 years. Participants can be on CSII or MDI treatment regimens to be eligible. After a run-in phase, subjects will be randomly assigned to one of the following two arms:

HCL arm: MiniMedTM 670G for 6 months; OR Conventional arm: MDI or CSII for 6 months.

Randomization will be stratified based on 4 variables: Time spent in target sensor glucose range (3.9 – 10mmol/L) – with participants evenly split above and below 55%(17) time in target range, age, diabetes duration, and centre site. This will be managed by the Clinical Trials Centre in Sydney.

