# Primary endpoint

The primary endpoint, average % time spent in target glycaemic range (sensor glucose level 3.9 - 10 mmol/l) during 6 months, will be analysed using Analysis of covariance (ANCOVA) adjusting for baseline percentage score and site. Least square means and least square mean differences and their associated 95% confidence intervals will be presented for each treatment group and between groups. In the event that data are not normally distributed the Mann–Whitney–Wilcoxon (Wilcoxon Rank-Sum) Test will be employed which tests the medians. In addition if data are skewed, bootstrap methods(21) will be used which allows for a non-parametric test of the arithmetic means. Bootstrap methods simply estimate the distribution of the statistic through resampling with replacement (many times) from the original data population. These methods will also be employed for average % CGM as outlined in the secondary objectives.

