# Sensitivity analysis

The primary endpoint analysis will be re-run with the PP population as a sensitivity analysis. Secondary endpoints.

Coefficient of variation will be reported for each group: bootstrap methods will be used to estimate variability as appropriate.

Rates of hospitalisations for severe hypoglycaemia and moderate hypoglycaemia as per participant log will be analysed as unadjusted incidence rates based on the Poisson distribution. Incidence rates and incidence rate differences will be presented with their associated 95% confidence intervals calculated as exact Poisson confidence limits(22). In addition, where

HCL outpatient Version Number:6.0 Version Date:15/07/2019 appropriate Poisson or negative binomial regression models will be fitted e.g. moderate hypoglycaemia events from the participant log. If there are a high proportion of zero counts, zero inflated Poisson (ZIP) or zero inflated negative binomial models (ZINB) will be considered. If counts are sparse then rates will be reported descriptively only. Number of hospitalisations due to diabetic ketoacidosis events and other safety outcomes will be tabulated and presented as n and %.

Continuous outcome measures (including psychosocial) collected at baseline and endpoint will be analysed using ANCOVA adjusting for baseline score and site. Measures collected at baseline, 3 months and endpoint (e.g. *HbA1c*, *Fasting capillary blood glucose*, *Mean CGM glucose*, *Hypoglycaemic Fear Survey-II Worry scale*, *Child State-Trait Anxiety Inventory*, *The Diabetes Treatment Satisfaction Questionnaire status and change version*, *Problem Areas in Diabetes, Impaired awareness of hypoglycaemia: GOLD SCORE, INSPIRE questionnaires*) will be analysed using mixed models repeated measures (MMRM) adjusting for baseline score (where appropriate), group, period (baseline, 3 months, 6 months) and site. A random intercept term for 'individual' will also be employed if deemed appropriate. Least square means and least square mean differences and their associated 95% confidence intervals will be presented for each group and between groups. Unstructured covariance matrix will be used unless other covariance structures are more appropriate as determined by the Bayesian information criteria (BIC). Human technology interaction and health care professional experiences and expectations analyses will be reported Exploratory; descriptive analysis.

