A separate economic analysis will be conducted. Using measures (e.g. QALYs calculated from the EQ-5D) collected during the trial.

Performance Parameters will be reported descriptively (n, % for categorical measures and n, mean, median, standard deviation, minimum and maximum for continuous measures)

Subgroup and exploratory analysis

Subgroup analysis will be performed to examine differences in treatment effect based on participant characteristics. Subgroup analysis will be treated as exploratory, with the intent of hypothesis generation. A treatment by subgroup interaction term will be included in the MMRM to assess differential effects by subgroup. Subgroup analyses may include (but not be limited to):

- Age
  - o <12 years
  - $\circ$  >12 years
- BMI category
  - 0 <18
  - $\circ$  18 25
  - o > 25
- Diabetes duration
  - o <6 years
  - o 6 years or longer
- HbA1c at baseline.
  - 0 <8%
  - o 8% or greater

A range of additional exploratory analyses will be conducted. These analyses may include (but not be limited to):

- Differential effects of intervention based on time of day
- Examination of time spent in various glycaemic ranges
- Finer-grained analysis of BGL patterns
- Relationship between CGM usage/adherence and outcomes
- Differences in effect size based on control treatment regimen

Techniques used for subgroup and exploratory analysis will depend upon the distribution of the outcome measure and will include presentation/comparison of unadjusted rates with Poisson confidences limits (or negative binomial models where overdispersion is indicated), measures of central tendency and dispersion, mixed modelling, analysis of covariance, and novel graphical presentation.

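### Baseline insulin regimen (MDI or CSII) defines the control treatment and a planned sub-analysis but is neither a minimisation factor nor a covariate; adjusting for it is a cheap, modest improvement

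*Protocol*

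**What the plan says.** **Allocation.** The synopsis (Study Design) reads: "Minimisation randomisation will be employed, stratifying by time in target glucose range 3.9-10 mmol/L, age, diabetes duration, and centre site". Section 7.1 agrees: "Randomization will be stratified based on 4 variables", and it names the same four. Regimen appears in neither place.

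**Comparator.** Section 7.1 defines the control as "Conventional arm: MDI or CSII for 6 months". The synopsis makes clear that control participants carry on with the therapy they already use. Regimen is an inclusion criterion (Section 7.4.1), so it is on record before randomisation.

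**Models.** In Section 7.3 the primary endpoint "will be analysed using Analysis of covariance (ANCOVA) adjusting for baseline percentage score and site". Secondary continuous outcomes measured at baseline and endpoint use the same form of ANCOVA. Outcomes measured three times use a mixed model "adjusting for baseline score (where appropriate), group, period (baseline, 3 months, 6 months) and site".

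**Where regimen is used.** Section 6.2.2 says: "A sub analysis of HCL vs. MDI and HCL vs. CSII is planned". The synopsis and Section 6.3 repeat this. Section 7.3 also lists, among exploratory analyses that may be done, "Differences in effect size based on control treatment regimen".

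**The concern.** Regimen is part of the structure of this trial. It determines the treatment a control participant receives. It also determines the run-in education (Visit 2) and, in the HCL arm, how soon closed loop starts. Under Visit 7, people coming from CSII start after 3 to 7 days of CGM, and people coming from MDI start 2 to 4 weeks after pump start. Later visits are mostly counted from Visit 7, so at the 13-week assessment former MDI users have had less closed-loop time.

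A baseline variable with this role would normally be balanced at allocation or adjusted for in the model. Here it is neither, so a chance difference between the arms in MDI share is not corrected by any specified step. Three things are at stake:

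- some precision in the primary and secondary comparisons;
- sensitivity of regimen-dependent endpoints to chance imbalance, for example needle use in the health-economic data;
- the standing of the two sub-analyses. The protocol does not say whether each uses only the HCL participants who came from that regimen or the whole HCL arm.

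**Working it through.** **Inputs from Section 7.2:** planned difference 10 points, SD 13, 85% power, two-sided 5%, 64 per arm, 80 per arm after 20% drop-out.

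**Assumed, because the protocol does not give them:** MDI share 30%, 50% or 70%; regimen effect on 26-week time in range, after adjustment for baseline, of 2, 5 or 8 points.

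**The plan's own figure.** 64/0.8 = 80 reproduces. The 64 per arm does not: 10 points, SD 13 and 85% power require 31 per arm (32 with the t distribution), so 64 matches a total. That is a separate matter. Below, 64 per arm is used only as the stated number analysed, giving SE = 13 × √(2/64) = 2.3 points.

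**Step 1: size of chance imbalance.** With 80 per arm and 50% MDI, the SD of the between-arm difference in MDI share is √(2 × 0.25/80) = 0.079, or 7.9 points. Hypergeometric probabilities, treating allocation as unrelated to regimen:

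| Per arm | MDI share | SD (points) | P(≥10 points) | P(≥15 points) |
|---|---|---|---|---|
| 80 | 30% or 70% | 7.3 | 0.23 | 0.06 |
| 80 | 50% | 7.9 | 0.27 | 0.08 |
| 64 | 30% or 70% | 8.1 | 0.18 | 0.08 |
| 64 | 50% | 8.9 | 0.22 | 0.11 |

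Minimising on the four listed factors does not reduce this if regimen is unrelated to them. If regimen is related to site, age, duration or time in range, the imbalance would be smaller.

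**Step 2: shift in the primary estimate.** Shift = regimen effect × imbalance.

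- At a 15-point imbalance: 2 × 0.15 = 0.3; 5 × 0.15 = 0.75; 8 × 0.15 = 1.2 points.
- At the mean absolute imbalance (0.8 × 7.9 = 6.3 points): 2 × 0.063 = 0.13; 5 × 0.063 = 0.3; 8 × 0.063 = 0.5 points.

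**Step 3: precision gained by adjusting (50% MDI).** Variance explained = effect² × 0.25, set against 13² = 169.

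- 2 points: 1/169 = 0.6%; SE falls by 1 − √0.994 = 0.3%.
- 5 points: 6.25/169 = 3.7%; SE falls by about 1.9%.
- 8 points: 16/169 = 9.5%; SE falls by about 4.9%.

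**Step 4: price of adjusting.** For imbalance d and MDI share q, variance inflation is 1/(1 − d²/[4q(1 − q)]). At a 20-point imbalance this is 1.04 (q = 50%) to 1.05 (q = 30%). At a typical imbalance (d = 0.089, q = 50%) it is about 1.008, or 0.4% in SE. The gain is therefore roughly cancelled if regimen matters by only 2 points, and is clearly positive at 5 to 8 points. Power for 10 points with 64 per arm and SD 13 is 0.992 without adjustment and 0.992 to 0.996 with the Step 3 reductions in variance.

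**Step 5: sub-analyses within baseline regimen.** With 64 × q per arm, power for a 10-point difference is:

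| Regimen's share | SD 13 | SD 15 |
|---|---|---|
| 30% | 66% | 54% |
| 50% | 87% | 76% |
| 70% | 95% | 88% |

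(15% is the baseline-adjusted SD that Section 7.2 also mentions.) Balance at allocation would fix how each regimen splits between the arms. It would not fix the regimen's overall share.

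**The case against.** The strongest reply is that nothing here is wrong. The two allocation statements agree, and choosing four factors rather than five is a legitimate preference. Randomisation keeps the comparison valid, and the variance due to an unadjusted covariate already sits in the residual error and so in the confidence interval. Baseline glycaemia is handled twice: 21 days of blinded CGM on the participant's own regimen supply both an allocation factor and the ANCOVA covariate. The run-in education comes before that CGM. The difference in closed-loop start affects only the HCL arm and is long past by weeks 23 to 26. If prior regimen matters mainly among controls, the shifts in Step 2 halve. A regimen-adjusted supplementary analysis may also be in an SAP not seen here.

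Most of this stands, and it is why the point is modest. It does not remove the point. The protocol writes out the covariate sets and allocation factors itself, and an SAP cannot change allocation already made. The exploratory item on control regimen is optional and looks at effect modification, so it corrects no imbalance.

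Three stronger readings might be inferred, and the documents support none of them:

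- **That the omission biases or could overturn the primary result.** Randomisation rules out bias, and 0.3 to 1.2 points cannot reverse a 10-point effect.
- **That the sub-analyses need a like MDI:CSII mix in the two arms.** Done within baseline regimen, each compares like with like whatever the mix; only group sizes are left to chance. Done with the whole HCL arm against one control regimen, even perfect balance would not make the groups comparable.
- **That sensor costs depend on regimen.** Sensor use follows the allocated arm: the exclusion criteria tie CGM use to study group, and the blinded CGM is scheduled alike for both control regimens. Needles do follow regimen in the control arm.

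**Conclusion.** The omission is real: regimen is in neither allocation statement and in none of the stated ANCOVA or mixed models. Its consequence for the primary endpoint is small, about 0.3 to 1.2 points at a 15-point imbalance (probability 0.06 to 0.11 across the cases in Step 1) and less at a typical one. The reduction in standard error is about 0.3 to 5% before the small price of the extra term. These sizes rest on an assumed regimen effect of 2 to 8 points after baseline adjustment, an assumed MDI share (50% for the precision figures) and the protocol's SD of 13. The effect on costs cannot be sized from the protocol. This is an inexpensive improvement in precision and robustness, not a threat to validity. The more useful part is to define the two regimen sub-analyses so that each stays a randomised comparison.

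**What to change.** 1. Add baseline regimen (MDI/CSII) as a covariate in the primary ANCOVA and in the secondary ANCOVA and mixed models. The variable is already recorded, so the cost is 1 df per model.
2. State that HCL vs MDI compares HCL and control participants who were on MDI at baseline, and that HCL vs CSII does the same for CSII. This costs a sentence in the protocol or SAP.
3. Only if allocation is still open, add regimen as a fifth minimisation factor, which is a configuration change. If allocation is complete, items 1 and 2 suffice.

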#### 2. Clinical measures

The compare the difference between HCL insulin delivery vs standard therapy for the following measures

- i) Change in auxological parameters (height, weight)
- ii) Change in total daily dose, including basal and bolus proportion, carbohydrate ratios and insulin sensitivity

#### 3. Psychosocial:

Questionnaires will be conducted on 3 occasions: at baseline, 13 weeks and 26 weeks.

- i. **Fear of hypoglycaemia**: Hypoglycaemic Fear Survey-II Worry scale: 17-<25years. Children's Hypoglycaemia Fear survey 12 – 17 years.
- ii. **Hypoglycaemia Awareness**: Hypoglycaemia Awareness Scale (Gold Score) (all ages)
- iii. **Anxiety**: State-Trait Anxiety Inventory (Child version for 12-15yrs, adult version ≥16-<25yrs)
- iv. **Impact and Satisfaction**: The Diabetes Treatment
  Satisfaction Questionnaire status and change version (16 <25years)
- v. **Quality of Life**: 12-<25years: EQ-5D-Y,
- vi. **Diabetes specific quality of life**: PedsQL-Child version (12 year olds), Adolescent version (13 18) and young adult version (18 <25).
- vii. **Diabetes distress:** Problem Areas in Diabetes (Teen version for 12 17 years, standard version  $\geq 17 \langle 25yr \rangle$
- viii. Participant reported outcome for Automated Delivery system: INSPIRE Questionnaires: baseline and post-assessment versions Child version (12 year olds), Adolescent version (13-18) and adult version(18-25)
- ix. **Semi structure interview** (all ages post study, PCH only)

## 4. Human-technology interaction:

To assess participant technology interaction and explore adherence patterns and approaches that may improve it. Repeated sampling methodology will be used. A series of questions will be asked once a week via a phone app, which will take less than 1 minute to complete.

#### 5. Health-economic

To assess the health economic impact of the MiniMedTM 670G Insulin Pump Hybrid Closed Loop System vs standard therapy (MDI and CSII). The following data points will be used as part of the economic analysis:

- i. QALYs calculated from the EQ-5D
- ii. Hypoglycaemic events and HbA1c
- iii. Participant reporting on work interruption
- iv. Investigator reporting time spent on training, education and

HCL outpatient Version Number: 6.0 Version Date: 15/07/2019

	symmetry the type of health professional resource year							
	strips, batteries, sensors, site dressings, lancets, needlinsulin).  6. Biomarkers (all ages)  Fo assess the impact of the MiniMed™ 670G Insulin Pump Hybrid Closed Loop System Vs standard therapy (MDI and CSI on the biomarkers listed below. Biomarkers will be tested from blood and urine samples at baseline, and 26 weeks post andomisation.  i. Cell Adhesion Molecules (CAM)S  iii. Soluble vascular cell adhesion molecules sVCAM iii. Soluble intercellular adhesion molecules sICAM v. Oxidized Low density lipoprotein vi. Myeloperoxidase.  vii. MicroRNA signatures for arterial, renal and retinal complications viii. Telomerase ix. DNA methylation/acetylation x. Glycomark xi. Isoprostanes and proteomics xiii. Clotting profile  7. Performance Parameters  Fo assess the performance of the MiniMed™ 670G Insulin Pum Hybrid Closed Loop System, and components. The following neasures will be used:  i. Proportion of time hybrid closed loop is active ii. Unplanned exits from closed loop (n)  iii. Sensor performance – mean absolute relative difference (MARD), sensor failures (n)  iv. Insulin delivery line performance – reported delivery line failures (n)  8. Health Care Providers experiences  To assess health care providers experiences and expectations of Hybrid Closed Loop insulin delivery.  Fine % time sensor glucose is in target range (3.9–10 mmol/L) luring HCL insulin delivery vs standard therapy (MDI and CSII measured 23-26 weeks post-randomisation.							
	insulin).							
	6. Biomarkers (all ages)							
	T 4 ' C4 M' 'M ITM (70C I 1' D							
	v. Diabetes management consumables (glucose strips, ketone strips, batteries, sensors, site dressings, lancets, needles, insulin).  6. Biomarkers (all ages)  To assess the impact of the MiniMed™ 670G Insulin Pump Hybrid Closed Loop System Vs standard therapy (MDI and CSII) on the biomarkers listed below. Biomarkers will be tested from blood and urine samples at baseline, and 26 weeks post randomisation.  i. Cell Adhesion Molecules (CAM)S  ii. Soluble vascular cell adhesion molecules sVCAM  iii. Soluble intercellular adhesion molecules sICAM  iv. s-e Selectin  v. Oxidized Low density lipoprotein  vi. Myeloperoxidase.  vii. MicroRNA signatures for arterial, renal and retinal complications  viii. Telomerase  ix. DNA methylation/acetylation  x. Glycomark  xi. Isoprostanes and proteomics  xiii. Clotting profile  7. Performance Parameters  To assess the performance of the MiniMed™ 670G Insulin Pump Hybrid Closed Loop System, and components. The following measures will be used:  i. Proportion of time hybrid closed loop is active  ii. Unplanned exits from closed loop (n)  iii. Sensor performance – mean absolute relative difference (MARD), sensor failures (n)  iv. Insulin delivery line performance – reported delivery line failures (n)  8. Health Care Providers experiences  To assess health care providers experiences and expectations of Hybrid Closed Loop insulin delivery.  The % time sensor glucose is in target range (3.9–10 mmol/L) during HCL insulin delivery vs standard therapy (MDI and CSII), measured 23-26 weeks post-randomisation.							
	v. Diabetes management consumables (glucose strips, ketone strips, batteries, sensors, site dressings, lancets, needles, insulin).  6. Biomarkers (all ages)  To assess the impact of the MiniMed™ 670G Insulin Pump Hybrid Closed Loop System Vs standard therapy (MDI and CSII) on the biomarkers listed below. Biomarkers will be tested from blood and urine samples at baseline, and 26 weeks post randomisation.  i. Cell Adhesion Molecules (CAM)S  ii. Soluble vascular cell adhesion molecules sVCAM iii. Soluble intercellular adhesion molecules sICAM v. s-e Selectin v. Oxidized Low density lipoprotein vi. Myeloperoxidase. vii. MicroRNA signatures for arterial, renal and retinal complications viii. Telomerase ix. DNA methylation/acetylation x. Glycomark xi. Isoprostanes and proteomics xii. Clotting profile  7. Performance Parameters  To assess the performance of the MiniMed™ 670G Insulin Pump Hybrid Closed Loop System, and components. The following measures will be used:  i. Proportion of time hybrid closed loop is active ii. Unplanned exits from closed loop (n)  iii. Sensor performance – mean absolute relative difference (MARD), sensor failures (n)  8. Health Care Providers experiences  To assess health care providers experiences and expectations of Hybrid Closed Loop insulin delivery.  The % time sensor glucose is in target range (3.9–10 mmol/L) during HCL insulin delivery vs standard therapy (MDI and CSII), measured 23-26 weeks post-randomisation.  1. Glycaemic:  i. CGM data:  a. % CGM Time <2.8 mmol/L							
	
 
v. Diabetes management consumables (glucose strips, ketone strips, batteries, sensors, site dressings, lancets, needles, insulin).
 
6. Biomarkers (all ages)
 
To assess the impact of the MiniMed™ 670G Insulin Pump Hybrid Closed Loop System Vs standard therapy (MDI and CSII) on the biomarkers listed below. Biomarkers will be tested from blood and urine samples at baseline, and 26 weeks post randomisation. 
 
i. Cell Adhesion Molecules (CAM)S
 
ii. Soluble vascular cell adhesion molecules sVCAM
 
iii. Soluble intercellular adhesion molecules sICAM
 
iv. se Selectin
 
v. Oxidized Low density lipoprotein
 
vi. Myeloperoxidase.
 
vii. MicroRNA signatures for arterial, renal and retinal complications
 
viii. Telomerase
 
ix. DNA methylation/acetylation
 
x. Glycomark
 
xi. Isoprostanes and proteomics
 
xii. Clotting profile
 
 
 
7. Performance Parameters
 
To assess the performance of the MiniMed™ 670G Insulin Pump Hybrid Closed Loop System, and components. The following measures will be used: 
 
i. Proportion of time hybrid closed loop is active
 
ii. Unplanned exits from closed loop (n)
 
iii. Sensor performance — mean absolute relative difference (MARD), sensor failures (n)
 
iv. Insulin delivery line performance — reported delivery line failures (n)
 
8. Health Care Providers experiences
 
To assess health care providers experiences and expectations of Hybrid Closed Loop insulin delivery.
 
 
 
The % time sensor glucose is in target range (3.9–10 mmol/L) during HCL insulin delivery vs standard therapy (MDI and CSII), measured 23-26 weeks post-randomisation.
 
1. Glycaemic: 
 
i. CGM data:
 
 
 
							
	
 
v. Diabetes management consumables (glucose strips, ketone strips, batteries, sensors, site dressings, lancets, needles, insulin).
 
6. Biomarkers (all ages)
 
To assess the impact of the MiniMed™ 670G Insulin Pump Hybrid Closed Loop System Vs standard therapy (MDI and CSII) on the biomarkers listed below. Biomarkers will be tested from blood and urine samples at baseline, and 26 weeks post randomisation.  i. Cell Adhesion Molecules (CAM)S  ii. Soluble vascular cell adhesion molecules sVCAM  iii. Soluble intercellular adhesion molecules sICAM  iv. s-e Selectin  v. Oxidized Low density lipoprotein  vi. Myeloperoxidase.
 
vii. MicroRNA signatures for arterial, renal and retinal complications
 
viii. Telomerase  ix. DNA methylation/acetylation  x. Glycomark  xi. Isoprostanes and proteomics  xiii. Clotting profile
 
7. Performance Parameters
 
To assess the performance of the MiniMed™ 670G Insulin Pump Hybrid Closed Loop System, and components. The following measures will be used:  i. Proportion of time hybrid closed loop is active  ii. Unplanned exits from closed loop (n)  iii. Sensor performance – mean absolute relative difference (MARD), sensor failures (n)
 
iv. Insulin delivery line performance – reported delivery line failures (n)
 
8. Health Care Providers experiences
 
To assess health care providers experiences and expectations of Hybrid Closed Loop insulin delivery.
 
The % time sensor glucose is in target range (3.9–10 mmol/L) during HCL insulin delivery vs standard therapy (MDI and CSII), measured 23-26 weeks post-randomisation.
 
1. Glycaemic:
 
							
	v. Diabetes management consumables (glucose strips, ketone strips, batteries, sensors, site dressings, lancets, needles, insulin).  6. Biomarkers (all ages)  To assess the impact of the MiniMed™ 670G Insulin Pump Hybrid Closed Loop System Vs standard therapy (MDI and CSII) on the biomarkers listed below. Biomarkers will be tested from blood and urine samples at baseline, and 26 weeks post randomisation.  i. Cell Adhesion Molecules (CAM)S  ii. Soluble vascular cell adhesion molecules sVCAM iii. Soluble intercellular adhesion molecules sICAM iv. s-e Selectin  v. Oxidized Low density lipoprotein vi. Myeloperoxidase. vii. MicroRNA signatures for arterial, renal and retinal complications  viii. Telomerase ix. DNA methylation/acetylation x. Glycomark xi. Isoprostanes and proteomics xii. Clotting profile  7. Performance Parameters  To assess the performance of the MiniMed™ 670G Insulin Pump Hybrid Closed Loop System, and components. The following measures will be used:  i. Proportion of time hybrid closed loop is active ii. Unplanned exits from closed loop (n)  iii. Sensor performance — mean absolute relative difference (MARD), sensor failures (n)  iv. Insulin delivery line performance — reported delivery line failures (n)  8. Health Care Providers experiences  To assess health care providers experiences and expectations of Hybrid Closed Loop insulin delivery.  The % time sensor glucose is in target range (3.9–10 mmol/L) during HCL insulin delivery vs standard therapy (MDI and CSII), measured 23-26 weeks post-randomisation.  1. Glycaemic:  i. CGM data:  a. % CGM Time <2.8 mmol/L							
	v. Diabetes management consumables (glucose strips, ketone strips, batteries, sensors, site dressings, lancets, needles, insulin).  6. Biomarkers (all ages)  To assess the impact of the MiniMed™ 670G Insulin Pump Hybrid Closed Loop System Vs standard therapy (MDI and CSII) on the biomarkers listed below. Biomarkers will be tested from blood and urine samples at baseline, and 26 weeks post randomisation.  i. Cell Adhesion Molecules (CAM)S  ii. Soluble vascular cell adhesion molecules sVCAM iii. Soluble intercellular adhesion molecules sICAM iv. s-e Selectin  v. Oxidized Low density lipoprotein  vi. Myeloperoxidase.  vii. MicroRNA signatures for arterial, renal and retinal complications  viii. Telomerase  ix. DNA methylation/acetylation  x. Glycomark  xi. Isoprostanes and proteomics  xii. Clotting profile  7. Performance Parameters  To assess the performance of the MiniMed™ 670G Insulin Pump Hybrid Closed Loop System, and components. The following measures will be used:  i. Proportion of time hybrid closed loop is active  ii. Unplanned exits from closed loop (n)  iii. Sensor performance − mean absolute relative difference (MARD), sensor failures (n)  iv. Insulin delivery line performance − reported delivery line failures (n)  8. Health Care Providers experiences  To assess health care providers experiences and expectations of Hybrid Closed Loop insulin delivery.  The % time sensor glucose is in target range (3.9–10 mmol/L) during HCL insulin delivery vs standard therapy (MDI and CSII), measured 23-26 weeks post-randomisation.							
	iv. s-e Selectin							
	Hybrid Closed Loop System Vs standard therapy (MDI and CSII) on the biomarkers listed below. Biomarkers will be tested from blood and urine samples at baseline, and 26 weeks post randomisation.  i. Cell Adhesion Molecules (CAM)S  ii. Soluble vascular cell adhesion molecules sVCAM  iii. Soluble intercellular adhesion molecules sICAM  iv. s-e Selectin  v. Oxidized Low density lipoprotein  vi. Myeloperoxidase.  vii. MicroRNA signatures for arterial, renal and retinal complications  viii. Telomerase  ix. DNA methylation/acetylation  x. Glycomark  xi. Isoprostanes and proteomics  xii. Clotting profile  7. Performance Parameters  To assess the performance of the MiniMed™ 670G Insulin Pump Hybrid Closed Loop System, and components. The following measures will be used:  i. Proportion of time hybrid closed loop is active  ii. Unplanned exits from closed loop (n)  iii. Sensor performance — mean absolute relative difference (MARD), sensor failures (n)  iv. Insulin delivery line performance — reported delivery line failures (n)  8. Health Care Providers experiences  To assess health care providers experiences and expectations							
	
 
v. Oxidized Low density lipoprotein
 
vi. Myeloperoxidase.
 
vii. MicroRNA signatures for arterial, renal and retinal complications
 
viii. Telomerase
 
ix. DNA methylation/acetylation
 
x. Glycomark
 
xi. Isoprostanes and proteomics
 
xii. Clotting profile
 
7. Performance Parameters
 
To assess the performance of the MiniMedTM 670G Insulin Pump
 
Hybrid Closed Loop System, and components. The following
 
							
	
 
iv. s-e Selectin
 
v. Oxidized Low density lipoprotein
 
vi. Myeloperoxidase.
 
vii. MicroRNA signatures for arterial, renal and retinal complications
 
viii. Telomerase
 
ix. DNA methylation/acetylation
 
x. Glycomark
 
xi. Isoprostanes and proteomics
 
xii. Clotting profile
 
7. Performance Parameters
 
To assess the performance of the MiniMedTM 670G Insulin Pump Hybrid Closed Loop System, and components. The following measures will be used:
 
							
	strips, batteries, sensors, site dressings, lancets, needles, insulin).  6. Biomarkers (all ages)  To assess the impact of the MiniMed™ 670G Insulin Pump Hybrid Closed Loop System Vs standard therapy (MDI and CSII) on the biomarkers listed below. Biomarkers will be tested from blood and urine samples at baseline, and 26 weeks post randomisation.  i. Cell Adhesion Molecules (CAM)S  ii. Soluble vascular cell adhesion molecules sVCAM  iii. Soluble intercellular adhesion molecules sICAM  iv. s-e Selectin  v. Oxidized Low density lipoprotein  vi. Myeloperoxidase.  vii. MicroRNA signatures for arterial, renal and retinal complications  viii. Telomerase  ix. DNA methylation/acetylation  x. Glycomark  xi. Isoprostanes and proteomics  xii. Clotting profile  7. Performance Parameters  To assess the performance of the MiniMed™ 670G Insulin Pump Hybrid Closed Loop System, and components. The following measures will be used:  i. Proportion of time hybrid closed loop is active  ii. Unplanned exits from closed loop (n)  iii. Sensor performance — mean absolute relative difference (MARD), sensor failures (n)  iv. Insulin delivery line performance — reported delivery line failures (n)  8. Health Care Providers experiences  To assess health care providers experiences and expectations of Hybrid Closed Loop insulin delivery.  The % time sensor glucose is in target range (3.9–10 mmol/L) during HCL insulin delivery vs standard therapy (MDI and CSII), measured 23-26 weeks post-randomisation.							
	viii. Telomerase ix. DNA methylation/acetylation x. Glycomark xi. Isoprostanes and proteomics							
	

ix. DNA methylation/acetylation

x. Glycomark

xi. Isoprostanes and proteomics

							
	*							
	•							
	7. Performance Parameters							
	-							
	To assess the performance of the MiniMed TM 670G Insulin Pumn							
	Hybrid Closed Loop System, and components. The following measures will be used:							
	Hybrid Closed Loop System, and components. The following measures will be used:							
	i. Proportion of time hybrid closed loop is active							
	ii. Unplanned exits from closed loop $(n)$							
	iii. Sensor performance – mean absolute relative difference							
	8. Health Care Providers experiences							
	To coope health come and down and the							
	of Hyorid Closed Loop insum denvery.							
Primary endpoint	The % time sensor glucose is in target range (3.9–10 mmol/L)							
Secondary endpoints								
